4. STATISTICAL CONSIDERATIONS AND METHOD OF ANALYSIS

4.1 *Sample Size*

The estimated minimum target recruitment for this study is 16 patients, based on the likelihood that data saturation has been achieved²⁰. If saturation has not been achieved, then the study will continue to recruit to a maximum of 30 patients.

4.2 *Method of analysis*

The anonymised transcripts will be uploaded to NVivo software, provided by the University of Glasgow. The interviews will then undergo thematic analysis to identify key attitudes to re-irradiation.

There is a quantitative element to this study, where patients are asked to rate the severity of side effects from radiotherapy (describing their side effects as either mild/moderate or severe) and if they would consider a second course of radiotherapy. These will be analysed using descriptive statistics and Chi-squared testing.

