3. METHODOLOGY

3.1. *Study design*

This is a qualitative interview study. The semi-structured qualitative interviews will take place after radiotherapy is completed and explore positive and negative aspects of that treatment, followed by discussion about concerns about re-irradiation, and risk of side-effects. Figure 1 provides an overview of the study design.

3.2. *Inclusion and Exclusion Criteria*

Patients must meet all of the following inclusion criteria to be considered for this study:

- Age 18 years old or above
- Pathological or radiological diagnosis of non-small cell lung cancer
- Undergoing radical radiotherapy to the thorax using the following fractionations (55 Gray in 20 fractions, 54 Gray in 36 fractions or any Stereotactic Ablative Body Radiotherapy (SABR) fractionation that delivers a biological effective dose of greater than 100Gy₁₀) as part of their primary lung cancer treatment at time of study enrolment
- Patients receiving concurrent and/or adjuvant systemic therapies are permitted
- Radiotherapy is delivered in the Beatson West of Scotland Cancer Centre
- Signed, written informed consent
- Willing and able to complete study processes

Patients who meet any of the following exclusion criteria will not be enrolled on to the study:

- Not fluent in English

3.3. *Recruitment and sampling*

In order to ensure adequate representation of patients receiving systemic treatment and different types of radiotherapy (as their experience of treatment will vary considerably), four patients will be recruited from each of the following radiotherapy sub-types: SABR, Continuous hyperfractionated accelerated radiotherapy CHART, concurrent chemoradiotherapy and radiotherapy alone.

For patients undergoing SABR, they will be approached by a radiographer at their mould room appointment, where the aims of the study and the study procedures will be explained, and participant information sheet will be given to them. They will then have approximately 3 weeks to consider this information. When they return to have their radiotherapy, the radiographer will enquire if they wish to be involved in this study. If so, they will be seen by the researcher for consent on the same day.

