Patients receiving CHART, concurrent chemoradiotherapy, or radiotherapy alone, will be recruited through the on-treatment review clinic. This clinic at the Beatson West of Scotland Cancer Centre is where patients having radical radiotherapy are monitored every week during their treatment. It is staffed by clinical nurse specialists and radiographers. They will pre-screen new patients attending their first/second on-treatment review clinic during the first

two weeks of radical radiotherapy. Patients who meet the inclusion criteria will be approached by the clinical nurse specialist/radiographer in the clinic. The aim of the study and the study rationale will be described and an information sheet will be given to the patients (see Appendix B).

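### Does the protocol need a rule for spreading patients 17 to 30 over the four radiotherapy sub-types?

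*Protocol*

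**What the plan says.** Section 3.3 of the protocol gives the purpose of the quotas as follows: "In order to ensure adequate representation of patients receiving systemic treatment and different types of radiotherapy". It then states that "four patients will be recruited from each of the following radiotherapy sub-types: SABR, Continuous hyperfractionated accelerated radiotherapy CHART, concurrent chemoradiotherapy and radiotherapy alone". SABR patients are approached at their mould room appointment. The other three sub-types share one route: "Patients receiving CHART, concurrent chemoradiotherapy, or radiotherapy alone, will be recruited through the on-treatment review clinic".

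Section 4.1 reads: "The estimated minimum target recruitment for this study is 16 patients, based on the likelihood that data saturation has been achieved". It continues: "If saturation has not been achieved, then the study will continue to recruit to a maximum of 30 patients".

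On eligibility, section 3.2 says: "Patients receiving concurrent and/or adjuvant systemic therapies are permitted". Section 4.2 makes thematic analysis the main method. For the side-effect ratings and the willingness question it adds: "These will be analysed using descriptive statistics and Chi-squared testing".

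**The concern.** Section 3.3 gives four per sub-type without saying whether that is a target or a minimum, while section 4.1 lets the study grow to 30. Read strictly, the quota covers only the first 16 patients. The protocol's reason for the quota, that experience differs greatly between treatments, does not lapse at patient 16. The extra patients could then come from whichever clinic recruits most easily, and the severity and willingness counts in section 4.2 would be summarised over that mix.

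The sub-types also do not obviously cover everyone whom section 3.2 admits. A patient with adjuvant but no concurrent systemic therapy is not a concurrent chemoradiotherapy patient and may not be a radiotherapy-alone patient either. If so, an eligible patient has no cell to count in.

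At stake is whether an extended sample would still represent the treatment types that the protocol set out to represent.

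**Working it through.** **Inputs.** Four patients per sub-type and four sub-types (section 3.3); minimum 16 and maximum 30 (section 4.1). The protocol gives no error rate, power or effect size for this target, so only quota arithmetic applies.

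**The plan's own figure.** 4 × 4 = 16, which equals the stated minimum. Sections 3.3 and 4.1 agree.

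**Size of the open part.** 30 − 16 = 14 places, and 14/30 = 47% of the largest permitted sample.

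**Range the text permits, keeping four per sub-type.**
- Smallest share of one sub-type: 4/30 = 13%.
- Largest share, with all 14 extra places in one sub-type: (4 + 14)/30 = 18/30 = 60%.
- Share at 16: 4/16 = 25%.
- An even split of 30 is not possible (30/4 = 7.5); the nearest is 8, 8, 7 and 7.

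These are limits on what is allowed, not a forecast. Even at the extremes, every sub-type still has its four patients.

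**Would a rule narrow the range?** A near-equal split would. Directing extra interviews to the sub-types where new themes still emerge need not, because that rule can properly place all 14 in one sub-type and reach the same 60%. The second rule suits a study that extends for want of saturation. A wide range of shares is therefore not in itself a fault.

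**The adjuvant group.** Section 3.3 classifies by radiotherapy type.
- SABR with adjuvant therapy counts as SABR.
- CHART with adjuvant therapy counts as CHART.
- Section 3.2 lists three kinds of schedule. If 54 Gy in 36 fractions is CHART (an assumption, since the protocol does not say so), only 55 Gy in 20 fractions remains.
- Within that schedule, patients on concurrent chemotherapy have their own cell. The one unclear case is adjuvant without concurrent therapy.
- These patients are screened and consented during radiotherapy (sections 3.3 and 3.4), when they are receiving radiotherapy without concurrent treatment. The radiotherapy-alone cell is the natural place for them, though the text does not say so.

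**The case for a change.** The strongest case for a change is that the mix may alter the counts in section 4.2. Putting a size on this needs willingness rates that the protocol does not give. Assume that a share *a* of one sub-type and a share *b* of the others would consider a second course. The pooled share is then *b* + (*a* − *b*) × *k*/*N*, where *k* of the *N* patients belong to that sub-type.

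| Assumed *a*, *b* | 4 of 16 | 4 of 30 | 18 of 30 |
|---|---|---|---|
| 80%, 40% | 50% | 45% | 64% |
| 60%, 40% | 45% | 43% | 52% |

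The arithmetic is right, but it carries little weight here. The rates are invented, and the extremes need all 14 extra places, or none, to fall in one sub-type. The equal-quota figure is no truer than the others: four per sub-type is a sampling device, and nothing in the protocol presents a pooled percentage as an estimate for the patient population.

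It can also be said that the protocol does not state whether four means consents or completed interviews, whether losses are replaced, or whether saturation is judged overall or by sub-type. These are details left open rather than errors, and the room up to 30 allows losses to be made good.

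What stands is that no visible sentence allocates patients 17 to 30 or names the cell for the adjuvant-only patient on 55 Gy in 20 fractions. The study schema (Figure 1) is not reproduced in the text at hand, so even this holds only for what can be read.

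**Conclusion.** No change is called for. The quota and the minimum match at 16, and nothing in section 4.1 cancels the four per sub-type if recruitment continues. The open part is at most 14 of 30 places, and it arises only if saturation is not reached at 16. A qualitative researcher would then choose the next interviewees with the unsaturated themes and sub-types in view. Leaving that choice open is a fair trade-off, since a preset split could send interviews to sub-types that have nothing new to add.

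The unclear adjuvant case is confined to one schedule and has an evident home. Followed as written, the protocol still delivers the representation that section 3.3 describes, and its thematic conclusions do not depend on the exact mix.

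This rests on reading four as a floor, on 54 Gy in 36 fractions being CHART, and on the section 4.2 counts being taken as descriptions of the interviewed sample.

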2. AIMS AND OBJECTIVES

2.1 *Aims*

The aim of this study is to explore patients' experience of radical radiotherapy for lung cancer and their attitudes to having a second treatment.

2.2. *Primary Objectives*

- (1) Explore patients' feelings and concerns about having a second course of radiotherapy

2.3. *Secondary Objectives*

- (1) Identify factors that patients consider when deciding on potential treatments in the setting of locally recurrent lung cancer (including effect of COVID-19 on treatment choice)
- (2) Investigate how patients' acceptance of side effects changes with the different projected outcomes of re-irradiation
- (3) Explore the relationship between the toxicities patients experienced during radiotherapy and their attitudes to a second course of radiotherapy
- (4) Investigate patients' awareness of surveillance imaging after radical treatment and willingness for scans

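### Does the test of side-effect severity against willingness for re-treatment have to be stratified by radiotherapy sub-type?

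*Protocol*

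**What the plan says.** Section 3.3 sets a purposive quota: "four patients will be recruited from each of the following radiotherapy sub-types", namely SABR, CHART, concurrent chemoradiotherapy and radiotherapy alone. The reason given is heterogeneity, "as their experience of treatment will vary considerably".

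Section 4.1 sizes the study on data saturation, not on power: "The estimated minimum target recruitment for this study is 16 patients", and if saturation is not reached "the study will continue to recruit to a maximum of 30 patients".

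Section 4.2 makes thematic analysis the main method and adds a small quantitative element. In it "patients are asked to rate the severity of side effects from radiotherapy", "describing their side effects as either mild/moderate or severe", and also "if they would consider a second course of radiotherapy". Both items go to descriptive summaries and a chi-squared test. No table layout, stratifier or weighting is given.

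The test serves the third secondary objective in Section 2.3: "Explore the relationship between the toxicities patients experienced during radiotherapy and their attitudes to a second course of radiotherapy".

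**The concern.** The sampling treats sub-type as the main source of variation, and the only named test leaves it out. The natural reading is one 2x2 table over all patients. Sub-type could affect severity through the intensity of treatment. It could also affect willingness through burden, such as the number of visits or added chemotherapy. If it does both, a pooled association can appear or be masked with nothing going on inside any sub-type, and an effect of treatment type would be read as an effect of toxicity. Section 1.7 sets the question in the context of recruiting to a future re-irradiation trial, so a misreading could carry forward.

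A related worry is the pooled proportion willing. Under equal quotas it is an equally weighted average of four groups, not the clinic's case mix.

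**Working it through.** **The plan's own figure.** 4 sub-types x 4 patients = 16, which matches the minimum in Section 4.1. The protocol gives no alpha, power or effect size, so there is no power calculation to reproduce.

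**Assumed inputs.** The protocol gives no rates by sub-type, so all of these are assumptions. Severity and willingness are taken as independent inside each sub-type, and both as two-level.

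| | SABR | CHART | Chemoradiotherapy | Radiotherapy alone |
|---|---|---|---|---|
| Set 1, P(severe) | 0.10 | 0.40 | 0.70 | 0.30 |
| Set 1, P(willing) | 0.90 | 0.70 | 0.50 | 0.80 |
| Set 2, P(severe) | 0.05 | 0.50 | 0.80 | 0.30 |
| Set 2, P(willing) | 0.95 | 0.60 | 0.30 | 0.80 |

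**Pooled odds ratio, Set 1, equal quotas.**
- P(severe) = (0.10 + 0.40 + 0.70 + 0.30)/4 = 0.375
- P(willing) = (0.90 + 0.70 + 0.50 + 0.80)/4 = 0.725
- P(severe and willing) = (0.09 + 0.28 + 0.35 + 0.24)/4 = 0.24
- P(willing given severe) = 0.24/0.375 = 0.64
- P(willing given mild/moderate) = (0.725 - 0.24)/0.625 = 0.776
- Odds ratio = (0.64/0.36)/(0.776/0.224) = 0.51

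**Set 2.** P(severe) = 0.4125, P(willing) = 0.6625 and P(severe and willing) = 0.2069. The conditional probabilities are 0.5015 and 0.7755, and the odds ratio is 0.29.

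**False rejection by the pooled uncorrected chi-squared test** (nominal two-sided 5%, 40,000 simulated studies; quotas 4/4/4/4 at 16, and 7/7/8/8 assumed at 30):
- Set 1: about 10% at 16 and 14% at 30.
- Set 2: about 24% and 36%.
- Severity as in Set 1, but willingness 0.70 in every sub-type: odds ratio 1.0, rejection about 5% at both sizes.

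The last line decides the point. Variation in severity alone, which is close to what Section 3.3 asserts, creates no bias. The distortion comes only from the second assumption, that willingness also varies by sub-type apart from toxicity.

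**What stratification would buy.** An exact test stratified by sub-type, with four per stratum, was simulated with a true odds ratio of 0.1 inside every sub-type:
- The stratified test detects it in about 10% of studies. Its false rejection rate is about 0.4% to 0.5%, and on average only about two of the four strata carry any information.
- The pooled test detects it in about 60% (Set 1) and 76% (Set 2). Those figures include the confounding that acts in the same direction. Where only severity varies, so that the pooled test holds its 5% level, it detects about 34%.
- At 30 patients the stratified test does better, a little under one half, but the study reaches that size only if saturation fails.

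**Pooled willingness.** Set 1 gives 72.5% under equal quotas. With an assumed case mix of 50/5/15/30 it gives 0.50 x 0.90 + 0.05 x 0.70 + 0.15 x 0.50 + 0.30 x 0.80 = 80%. The protocol supplies no case mix, and if willingness is the same in every sub-type there is no shift.

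**The case for a change.** The strongest case for a change is that the protocol does more than leave detail open. It names a test, and that test takes no account of the heterogeneity that the sampling was built on. Section 1.5 lists transport to the centre and side effects of the first treatment among possible reasons for refusal, and burden plainly differs between regimens, so a path from sub-type to willingness outside toxicity is credible. The analysis as written could not tell confounding from a real link. Changing to Fisher's exact test would not help: in another strong scenario it still rejects falsely in 12.2% of studies at 16 patients and 23.4% at 30. Sub-type is known for every patient, so a breakdown costs nothing.

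Much of this stands. The pooled association may be confounded, and a reader of the results should be told so. Three things limit it:
- Where sub-type acts through toxicity, that is part of the relationship under study, not confounding. Only the burden path counts, and the protocol gives nothing on its size.
- Section 2.3 asks only to explore the relationship, and Section 1.7 asks whether patients with toxicities are less likely to want more treatment. A crude association answers that descriptive question, whatever the mechanism.
- The protocol plans no overall acceptance rate as an estimate for the clinic. The quotas are there to secure representation, so the objection to the pooled proportion is aimed at a result that is not promised.

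**Conclusion.** No change to the plan is needed. The arithmetic behind the concern is correct: under the assumed rates, pooling can turn no association into an odds ratio of 0.51 or 0.29, with false rejection between 10% and 36%. Those figures rest wholly on sub-type rates for willingness that the protocol neither states nor implies. Without that variation the bias is nil.

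The formal remedy gives little at the planned minimum of 16, where four patients per stratum leave about a 10% chance of detecting even a tenfold difference in odds. Preferring the crude test or the stratified one is a fair trade-off between possible bias and almost no information. What is useful is to show severity and willingness by sub-type, call any pooled association exploratory and possibly confounded, and not present pooled willingness as the clinic's acceptance rate. The planned descriptive analysis already allows this, and a competent analyst would do it. It is unstated detail for one exploratory secondary objective of a qualitative study whose main method is thematic analysis. Whether chi-squared suits tables this small is a separate question and does not affect this conclusion.

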1.7. Relationship of symptoms from initial radiotherapy and willingness for re-treatment

Joseph *et al.*, when reporting a re-irradiation workshop, stated that patients who tolerated initial radiotherapy poorly were unsuitable for re-irradiation¹⁷. This refers to clinicians' concerns of causing severe toxicity with re-irradiation and may be a barrier to successful trial recruitment. Historically, re-irradiation has a significant risk of toxicity. The rates of severe toxicity may be lower using the newly published cumulative dose constraints, although these need validation. There are no prospective published data regarding whether patients who have toxicities are less likely to want further treatment. There is a need to identify if there is a relationship between the severity of patients' symptoms during initial treatment and their willingness for re-irradiation. This study will explore whether, despite toxicities from first the first radiotherapy course, patients still would consider aggressive re-treatment, and if so, what changes would they want to make their second course of radiotherapy more tolerable.

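### Protocol section 4.2 fixes chi-squared testing in a study planned at 16 patients, where no 2x2 table can reach an expected count of 5 in every cell; an exact test, or no test, fits better

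*Protocol*

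**What the plan says.** Section 4.2 describes a quantitative element alongside the thematic analysis. Patients rate their side effects as mild/moderate or severe and say whether they would consider radiotherapy again. Of these answers it says: "These will be analysed using descriptive statistics and Chi-squared testing". The protocol names no exact test, continuity correction, rule for small counts or significance level.

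On size, section 4.1 says: "The estimated minimum target recruitment for this study is 16 patients, based on the likelihood that data saturation has been achieved". If saturation is not reached, "the study will continue to recruit to a maximum of 30 patients". Section 3.3 gives the quota behind the 16: "four patients will be recruited from each of the following radiotherapy sub-types", with four sub-types listed.

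The question that the test would answer is secondary objective 3 in section 2.3: "Explore the relationship between the toxicities patients experienced during radiotherapy and their attitudes to a second course of radiotherapy". Section 1.7 gives the same reason for the study, a possible link between the severity of "symptoms during initial treatment and their willingness for re-irradiation".

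**The concern.** The chi-squared p-value is a large-sample approximation. The usual condition for relying on it is an expected count of at least 5 in each cell. With 16 patients in four cells the average expected count is only 4, so the protocol commits to a test whose usual condition it cannot meet at its own planned size, whatever the patients answer.

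At stake is a p-value below 5% for severity against willingness where an exact calculation gives no such support. The findings are meant to shape a later re-irradiation trial, so a spurious statement that patients with worse side effects are less willing (or more willing) could carry forward.

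**Working it through.** **Inputs.** Planned size 16 and maximum 30 (section 4.1). The quota reproduces the 16: 4 sub-types x 4 patients = 16 (section 3.3). Assumptions, because the protocol is silent: a 2x2 table with willingness as yes/no; a two-sided 5% level; an uncorrected Pearson test; and, for averaged rates, independent binomial splits with the smaller answer taking 10%, 20%, 30%, 40% or 50% on each question (25 combinations).

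**Step 1: can the condition be met?** Expected count = row total x column total / N. The smallest expected count is largest when both answers split as evenly as possible, which gives floor(N/2)² / N.

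| N | Largest attainable smallest expected count | Pairs of margins with all expected counts at least 5 |
|---|---|---|
| 16 | 8 x 8 / 16 = 4.00 | 0 of 225 |
| 17 | 8 x 8 / 17 = 3.76 | 0 of 256 |
| 18 | 9 x 9 / 18 = 4.50 | 0 of 289 |
| 19 | 9 x 9 / 19 = 4.26 | 0 of 324 |
| 20 | 10 x 10 / 20 = 5.00 | 1 of 361 |
| 21 | 10 x 10 / 21 = 4.76 | 0 of 400 |
| 30 | 15 x 15 / 30 = 7.50 | 61 of 841 |

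The condition is impossible at 16 to 19 and at 21. At 20 it needs 10/10 by 10/10. At 30 the two smaller groups must multiply to at least 5 x 30 = 150. Neither can exceed 15, so each must be at least 10. The looser rule that up to 20% of cells may fall below 5 does not help, because one cell of four is already 25%.

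**Step 2: how likely is it to be met at 30?** The probability is 38% to 71% if both answers split between 40/60 and 50/50; 12% to 19% if one splits 30/70 and the other 40/60 to 50/50; and at most 3% if both split 30/70 or either is 20/80 or less even.

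**Step 3: one table.** Take 8 patients with severe and 8 with milder side effects, of whom 6 and 2 are willing.
- Pearson: 16 x (6 x 6 − 2 x 2)² / (8 x 8 x 8 x 8) = 16 x 1024 / 4096 = 4.00, p = 0.046.
- With continuity correction: 16 x (32 − 8)² / 4096 = 2.25, p = 0.134.
- Fisher: with these margins the 12,870 equally likely arrangements include 2 x (784 + 64 + 1) = 1,698 at least this extreme, so p = 1,698 / 12,870 = 0.132.

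That 13.2% is also the true false-positive rate of the uncorrected test when both answers split 8/8.

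**Step 4: true false-positive rate at nominal 5%.** This comes from the hypergeometric distribution for every pair of margins, averaged over the 25 combinations.

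| Test | N = 16 | N = 30 |
|---|---|---|
| Pearson, uncorrected | 1.4% to 7.1% | 2.9% to 5.2% |
| Fisher's exact | 0.4% to 2.4% | 1.0% to 2.9% |
| Continuity-corrected | 0.1% to 1.3% | – |

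(Fisher's lower end at 16 counts p of exactly 0.05 as significant.) At 16 the Pearson rate is highest when both answers split evenly. For fixed margins it runs from 0% to 18.75%. The maximum needs smaller groups of 1 and 3, where a 3/16 chance event gives p = 0.032.

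**Step 5: disagreement between tests at 16.** Up to relabelling there are 268 tables, and Pearson calls 92 significant. Fisher's p is above 0.05 for 30 of these and exactly 0.05 for 2 more. This counts tables and is not an error rate.

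**The case against.** The strongest reply is that the count-of-5 rule is only a rule of thumb. At 30 patients the condition often fails, yet the averaged Pearson rate never exceeds 5.2%. At 16, only 9 of the 25 combinations exceed 5% and only 4 exceed 6%, all with both answers split between 40/60 and 50/50. Over the same combinations Pearson departs from 5% by about 1.4 percentage points on average and Fisher by about 3.8. In an exploratory setting, exchanging mild inflation for steady conservatism is a trade-off. This stands: it limits the size of the point and is why reporting without a test is an equally good remedy.

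Second, section 4.2 does not say that the test is uncorrected. With a continuity correction, no table at 16 would be significant that Fisher's test does not also call significant, and the false-positive concern disappears. That is true, but the protocol states no correction, and a correction leaves the expected counts as they are. An SAP, not seen here, might settle it; the test itself is fixed in the protocol.

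Third, the table shape is assumed. The severity wording could mean three levels, and the interview schedule was not available. Three levels make the table sparser: no 3x2 table meets even the looser 20% rule at 16, and only one set of margins does at 30.

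Last, this is a qualitative study sized for saturation, with no decision rule on this test. That is accepted and reflected in the weight given below.

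**Conclusion.** The point holds. At the planned 16 patients the usual condition for the named test fails for every possible 2x2 result. This is plain arithmetic, and needs only the assumption that both answers have two levels. It does not extend to the whole permitted range: from 20 patients the condition can be met (except at 21), though at 30 only when both answers split fairly evenly.

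The effect on error rates is modest and concentrated at the minimum: up to 7.1% averaged and 13.2% for the most even split, against an assumed nominal 5% with an uncorrected test. At 30 patients the averaged rate is close to or below nominal. The primary objective and most of secondary objective 3 rest on the interviews and thematic analysis, so the consequence is minor to moderate. It should be fixed because the defect is certain at the planned size and the repair is nearly free.

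**What to change.** In section 4.2, replace chi-squared testing with Fisher's exact test, reported with the cross-table of severity by willingness and labelled as an exploratory supplement to the thematic analysis. State whether severity has two levels or three; the exact test extends to a 3x2 table. Giving the cross-table alone, with no test, would also remove the fault.

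The cost is one sentence, with no extra patients or data. Fisher's test is conservative at these sizes (the rates are in Step 4), so p-values will usually be larger and a real relationship is easier to miss. A non-significant result should therefore not be read as evidence that severity and willingness are unrelated.
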